#### EXCLUSION CRITERIA

- 1. Unable to self quarantine for 72 hours if in the CPAP arm
- 2. Preexisting pulmonary diseases such as advanced COPD, advanced parenchymal lung disease, history of pneumothorax etc.
- 3. Claustrophobic and unable to tolerate CPAP mask
- 4. Evidence of hypercapnia
- 5. Recent heart of lung surgery within 3 months
- 6. Individuals without access to smart phones or wireless connection or internet access
- 7. Prior history of aspiration
- 8. Speech or swallowing impairment (risk of aspiration)
- 9. History of stroke with significant neurologic deficit
- 10. Advanced symptomatic heart failure
- 11. Unable to provide informed consent
- 12. Household with young children and child care responsibilities
- 13. Household with high-risk individuals (defined as over 60 or with comorbidities (e.g. heart disease, diabetes, pulmonary)

#### 6 – INFORMED CONSENT

#### 6.1 INFORMED CONSENT OVERVIEW

Each coordinator is responsible for ensuring that informed consent is obtained from each participant according to the guidelines of the central IRB, and all applicable local hospital and regulatory requirements. The consent procedure will include ongoing review of vital status and hospitalizations

through regular review of the EMRs from the local medical center(s), as well as the request of records from outside medical institutions when hospitalizations are reported at those institutions. Specifically, the following must be accomplished during the informed consent process:

The participant must be informed that participation in the study is voluntary, and that refusal to participate will involve no penalty or loss of benefits;

- The participant must be informed that the study involves research;
- The participant must be informed of any alternative procedures;
- The participant must be informed of any reasonable foreseeable risks;
- The participant must be informed of any benefits of participating in the research;
- An outline of safeguards to protect confidentiality must be included, as well as an indication of which parties are allowed to review the record;
- The participant must be informed of their right to withdraw without penalty. This discussion should be balanced with a discussion of the effect/s withdrawals have on the study, and the responsibility that the participant has, within limits, to continue in the study if they decide to enroll:
- The participant must be informed of their right to have questions answered at any time, and should be given adequate time to consider the study obligations and discuss the study with family members or other prior to consenting;

#### INFORMED CONSENT ADMINISTRATION

After patients have verbally agreed to participate in the study, they will complete an e-consent. The research staff will walk the patient through the e-consent and explain the study, risks and benefits in detail to the participant. The Mount Sinai approved Phone Consent process will be utilized, including having a witness present or having the patient send back signed documents in the case a witness is not able to be present.

Once deemed eligible, the study coordinator will provide the participant with a copy of the ICF. The study coordinator will explain in lay persons' terms the nature of all procedures. After the participant has had a chance to ask questions, the ICFs must be signed and dated.

Ample time should be given to allow the participant to read the ICFs, process the information, and ask questions. If the participant wishes to take the ICFs home before reaching a decision, they may do so. At the subsequent visit, the PI and/or other investigator should answer any questions raised by the participant. The participant should be made aware of their responsibilities throughout the screening process, during the baseline visit, after the randomization assignment, and throughout the study period. The importance of continued follow-up should be stressed and balanced with a discussion of the effect of withdrawal on the study.

The ICFs must be signed and personally dated by the participant (if a witness is not present), and by the principal investigator or designated staff member obtaining consent. The staff member obtaining consent and signing the ICF does not need to be a physician. The participant should not be asked to sign the ICF if they have any doubts about enrolling, or if the study staff member believes that the participant does not understand what participation would involve. Under no circumstance is any study information to be collected or study procedures performed other than those described for screening in Section 4.3, before the participant has signed the ICF. The study coordinator will maintain the original, signed ICFs in the participant's Source Document Binder with other study documentation, and provide a copy of the signed ICFs to the participant who

should be urged to retain the document for future reference. To ensure confidentiality, the study coordinator will not send copies of the ICFs signed by the participant to the DCC or other core groups.

#### HIPAA AUTHORIZATION FORM

Medical records will be screened in order to identify eligible patients. We will only be contacting patients if they meet the inclusion criteria, thus would be unable to obtain HIPAA authorization from them prior to viewing PHI. We are requesting a waiver for recruitment purposes only and will obtain full HIPAA Authorization from subjects who sign the consent form.

#### MEDICAL INFORMATION

All patients will be within the Mount Sinai health system, and their medical records will be screened in order to identify eligible patients. Waivers and signing for full HIPAA authorization will be obtained.

#### 6.2 CONFIDENTIALITY

Confidentiality is strictly maintained throughout the study. All study personnel have been trained about the importance of confidentiality and steps toward guarding it have been incorporated. In order to protect the privacy interests of subjects, we will ensure that all data will be entered into a secure and password protected electronic database (REDCap, OnCore, Ripple). Only study-related personnel will have access to the data and subject identifiers. All data will be collected electronically. When coding data, subject names will be stored separately from all other data, and ID codes are substituted for subject names.

#### 6.3 ASSIGNMENT OF ID CODES

Each participant will be assigned an ID code upon consent. This code will be entered into Redcap and will be used for all communication purposes. Only the PI, Research manager, and research coordinator will be able to link ID codes to each participant.

#### 7.1 VISIT SCHEDULE

#### Study Procedures:

- 1) Patients will be screened as described earlier
- 2) Eligible patients will be provided a flyer by ED provider when possible but may also be contacted by telephone once they have been discharged. (Of note: we are being approached by patients who are discharged from the hospital with COVID pneumonia who continue to experience shortness of breath and are requesting a CPAP without having prior knowledge of this study).
- 3) Research will be introduced to the patient, and if they agree to participate, a telephone consent will be conducted (according to IRB requirements including witness). Once patients have enrolled in the study, their PMD will also be notified of their participation. The patient will also be added to the study on EPIC, so that all treating physicians are aware of the patient's participation in our study.
- 4) Once patients have enrolled in the study, a pulse oximeter and a disposable WatchPAT One device will be mailed to the patients (within 24-48 hours of discharge). Orders placed before noon will be delivered the same day by a local durable medical equipment company we are working with. Orders placed past noon, CPAP delivery will be done the subsequent day or upto 48 hours if outside the New York area. Patients who are randomized to the treatment arm will receive a CPAP machine and three full-face masks in addition to the above noted equipment.
- 5) Patient will then be instructed via facetime or other video platform on CPAP setup and use, face mask fitting (those randomized to CPAP), and use of the WatchPAT One and pulse oximeter (for both CPAP and control arm). All participants will wear the WatchPAT one for one night whereas the oximeter will stay on continuously and the patient will report the saturation to us via follow up survey.
- 6) Patients randomized to receive CPAP will be asked to stay in isolation throughout the duration of the study i.e. 72 hours. They will be required to stay in a different room with the door shut and windows open (weather permitting). We will also ask the patient to stop using CPAP during meals or other daily activities. Subjects not on CPAP machine will also be instructed to sleep in a room with windows open (weather permitting).
- 7) Patients will use the CPAP machine as instructed for 72 hours.
- 8) All patients will be contacted every 6-12 hours to complete follow up assessments. These follow ups will be done via a phone call. If the timing of these follow ups fall between 10pm-6am, the follow up will be deferred until after 6am. After 72 hours, all patients will then be contacted daily until day 14 from randomization. After day 14, research staff will continue to monitor the medical charts for any visits to the hospital. One last contact will be made on day 28.
- 9) After 72 hours, patients will be asked to discontinue using the CPAP and pulse oximeter. If patients wish to continue to use the CPAP, they may do so for up to 7 days from time of randomization.
- 10) The research staff will continue to call all patients daily (after the 72 hour mark) to assess symptoms.
- 11) The patients can also choose to monitor their oxygen saturation beyond the 72 hours of treatment.
- 12) CPAP download is available continuously however we will download data on usage, pressure, leak daily and make adjustments to the mask or CPAP pressure as needed for patient comfort. For patients experiencing significant trouble tolerating high pressure, we will decrease CPAP from 8-10 cm to a fixed CPAP of 5 cm for 2-4 hours after which we will raise it back to 8-10cm for the

- duration of the study. If the patient is not able to tolerate the pressure again, we will reduce it back to 5cm of water pressure for several hours before increasing the pressure. This will be continued until the patient withdraws or 72 hours are completed, whichever occurs first.
- 13) Patients will be asked to track their own oxygen saturation using the provided pulse oximeter and report it when we contact them for the 6-12 hour follow up calls/surveys.
- 14) The sleep apnea test will provide continuous oxygen and breathing data for a period of 12 hours during the 72 hours and will also provide information on oxygen saturation while the patient is asleep.

The outline of the forms that correspond to the study visits can be found in the Appendix, Figure 1. All of these forms are subsequently included in the following appendicies.

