saturation and a disposable home sleep apnea monitor (WatchPAT) to track blood oxygen level continuously for 12 hours with data feed into a cloud based platform. Additionally, 100 patients will be randomized to receive CPAP at fixed pressure of 8 cm in women and 10cm in men and obese men and women will start be set at 10cm. of water pressure for 72 hours continuously (except for daily activities such as eating, grooming etc). We will adjust pressures in the range of 8-10cm depending on patient's comfort and related assessments in follow up period. However, the range of the pressure will remain constant throughout the study. While the study protocol will end at 72 hours, patients who wish to continue CPAP will be allowed to do so for symptomatic benefit up to 7 days from randomization. All CPAP recipients will be given a full-face mask and will be asked to stay in quarantine for the duration of the protocol to avoid risk of infecting family members with aerosol (information on this presented below). We hypothesize that early CPAP in COVID infected patients who have respiratory abnormalities will decrease the risk of subsequent hospitalization or death in 14 days from randomization.

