#### **OBJECTIVES**

Aim 1: Given the expected shortage of ventilators to treat COVID-19 suspected or confirmed individuals with severe acute respiratory distress syndrome (SARS)/ARDS, we propose a prospective, single-center, parallel group, open label, randomized clinical trial of CPAP (n=100) vs. control (n=100) in COVID-19 suspected or confirmed patients with abnormal chest x-ray or respiratory symptoms. The overarching aim of this proposal is to determine if early use of CPAP at home reduces the need for hospitalization admission or death in COVID-19 suspected or confirmed patients. We will include adult patients (age>18), oversampling when possible for obese patients who live alone or have more than one bedroom at home, with serologically confirmed or under investigation for acute COVID-19 infection, who have one or more of the following: fever (>38°C), sore throat, myalgia or flu-like illness AND have one or more of the following additional symptom or diagnostic criteria: abnormal chest x-ray, new onset cough, mild hypoxemia at rest (saturation less than 96%), abnormal lung exam, chest tightness or shortness of breath AND who are without need for hospital admission, i.e. being sent home. Patients with preexisting pulmonary diseases such as advanced COPD, advanced parenchymal lung disease, history of pneumothorax etc. will be excluded (see inclusion and exclusion criteria for more information). Participants in both arms will be shipped a pulse oximeter to monitor oxygen saturation and a disposable home sleep apnea monitor (WatchPAT) to track blood oxygen level continuously for 12 hours with data feed into a cloud based platform. Additionally, patients in the treatment arm (n=100) will be randomized to receive CPAP at fixed pressure: 8 cm water pressure in women and 10cm water pressure in men. All obese patients (BMI>=30) will be treated with a fixed pressure of 10cm of water pressure (both men and women). The CPAP pressure will be adjusted based on patient's comfort but will not deviate from the range of 8-10cm noted above. The treatment will be prescribed for 72 hours continuously (except for daily activities such as eating, grooming etc). While the study protocol will end at 72 hours, patients who wish to continue CPAP will be allowed to do so for symptomatic benefit up to 7 days. All CPAP recipients will be given a full-face mask and will be asked to stay in quarantine for the duration of the protocol to avoid risk of infecting family members with aerosol. We hypothesize that initiation of early CPAP in COVID infected patients with respiratory abnormalities will decrease the risk of subsequent hospitalization or death in 14 days from randomization. Patients will be followed for 28 days and as a secondary endpoint we will assess 28 day mortality as well as to assess for late impact of CPAP.

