#### **ENDPOINTS**

#### **Primary endpoint:**

The primary efficacy endpoint is a non-weighted composite endpoint comprised of the following components;

- All-cause mortality within 14 days of randomization
- Hospital Admission (including ED visit) within 14 days of randomization
- Oxygen saturation less than 90 during the 72-hour observation period from randomization
- Absolute reduction in oxygen saturation of more than 4% during the 72-hour observation period from randomization

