#### **Secondary endpoints:**

• Time to ICU admission within 14 days of randomization

- Time to intubation and mechanical ventilation within 14 days of randomization
- Time to death within 14 and 28 days of randomization
  - Degree of improvement in oxygen saturation within 14 days of randomization
  - Improvement in respiratory symptoms of cough, shortness of breath, etc via respiratory symptom questionnaire within 14 days of randomization
  - Adverse events and conversion rates of COVID family members in CPAP vs control within 14 days of randomization
  - Percent of patients electing to continue CPAP for greater than 72 hours
  - Time to hospital admission or ED visit within 14 days of randomization

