#### REPORTS

For each DMC meeting, interim safety reports including reports of all mortalities, household COVID conversions, and adverse events will be prepared by the trial statistical team. In addition to the prescheduled meetings, the DMC Chair will receive and review reports of all mortalities, unexpected serious adverse events, and COVID conversions within 72 hours of the Investigator becoming aware of the event as well.

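### Isolation of CPAP-arm patients is stated as 72 hours, but optional CPAP may run to day 7 and no visible sentence clearly carries the isolation instruction into that period

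*Protocol*

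**What the plan says.** **Isolation.** Section 7.1 item 6 states that CPAP-arm patients "will be asked to stay in isolation throughout the duration of the study i.e. 72 hours". Exclusion criterion 1 in Section 5.2 screens for ability to self-quarantine over the same 72 hours. Section 1.2 (Study Design) says: "All CPAP recipients will be given a full-face mask and will be asked to stay in quarantine for the duration of the protocol". Aim 1 repeats this and gives the reason: patients are "asked to stay in quarantine for the duration of the protocol to avoid risk of infecting family members with aerosol". Item 6 then adds a requirement to stay in a separate room with the door closed, and attaches no duration to it.

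**CPAP use.** Section 7.1 item 7 prescribes CPAP for 72 hours. Item 9 first asks patients to stop CPAP at that point, then adds: "If patients wish to continue to use the CPAP, they may do so for up to 7 days from time of randomization". Section 1.2 says the same: "While the study protocol will end at 72 hours, patients who wish to continue CPAP will be allowed to do so for symptomatic benefit". Continuation is a planned part of the trial. Section 7.6 schedules forms for patients on CPAP on days 4 to 7, and a secondary endpoint in Section 1.3 is "Percent of patients electing to continue CPAP for greater than 72 hours".

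**Household outcome.** Infection of family members within 14 days is a secondary endpoint (Section 1.3). The SAP compares it between arms with Fisher's exact test. Section 3.1 (Reports) says that "the DMC Chair will receive and review reports of all mortalities, unexpected serious adverse events, and COVID conversions within 72 hours" of the investigator learning of the event.

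**The concern.** The reason given for isolating CPAP patients is aerosol from the device. That reason applies on any day the device runs, including days 4 to 7. Yet every place that puts a number on isolation says 72 hours. The looser phrase in Section 1.2, which ties quarantine to the length of the protocol, does not help, because the same section says the protocol ends at 72 hours. Read as written, the explicit precaution can end while the source of the risk continues.

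Those exposed would be household members. Reporting conversions to the DMC Chair detects a transmission after it has happened, whereas the isolation instruction is meant to prevent it.

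**Working it through.** The plan gives no figure to reproduce. The check compares durations.

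**Inputs**
- End of permitted CPAP: 7 days from randomization (Sections 1.2 and 7.1 item 9), so 7 × 24 = 168 h.
- Length of stated isolation: 72 h (Section 7.1 item 6; Section 5.2, exclusion criterion 1).
- Start of isolation, *s* hours after randomization: not stated. It could be randomization (*s* = 0), which is how the primary endpoint counts its own 72 hours: "Oxygen saturation less than 90 during the 72-hour observation period from randomization". It could also be delivery of the device (*s* = *d*).
- Delivery delay *d*: same day up to 48 h (Section 7.1 item 4). I assume the order is placed at randomization; Section 7.3 puts the order directly after it.

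**Reading A: the closed-door sentence is tied to CPAP use.** The separate-room requirement then lasts as long as CPAP does. The uncovered time is 0 days.

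**Reading B: the closed-door sentence only elaborates the 72 hours.** The uncovered permitted time is 168 − (*s* + 72) hours.

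| Start of the 72 h | Delivery delay | Calculation | Uncovered permitted time |
|---|---|---|---|
| Randomization | 0, 24 or 48 h | 168 − 72 | 96 h (4 days) |
| Delivery | 0 h | 168 − 0 − 72 | 96 h (4 days) |
| Delivery | 24 h | 168 − 24 − 72 | 72 h (3 days) |
| Delivery | 48 h | 168 − 48 − 72 | 48 h (2 days) |

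Counted from randomization, the result does not depend on the delay, because the device arrives before hour 72 in every case.

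These are hours in which use is permitted. They are not hours of use, and they are not infections. The documents give no continuation rate, no share of patients living with others and no added transmission risk from CPAP, so the calculation cannot go further.

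**The case against.** The strongest defence has four parts.

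1. **The default is to stop.** The plan matches 72 hours of isolation to 72 hours of prescribed CPAP and then asks patients to discontinue. This stands, and it narrows the group to those who decline that request and also live with others. It does not close the gap, because item 9 attaches no isolation condition to continuing.

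2. **The closed-door sentence has no time limit.** The sentences after it deal with CPAP use itself (pausing for meals) and with patients not on the machine, which supports tying it to use. On the other side, it directly follows the 72-hour instruction and can be read as explaining it. Both readings are fair, so the range has to start at 0 days. A household precaution should not depend on which one a coordinator adopts.

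3. **Instructions may stand elsewhere.** Patients are taught by video call, and the CPAP set-up and use forms and the consent pages are not visible. This also stands: the point covers only the text that can be read. If those materials do extend isolation, the protocol should agree with them.

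4. **Other safeguards continue.** A reader might infer that household protection ends altogether at 72 hours. The documents do not support that. The full-face mask stays with the machine, usage and leak are downloaded daily, and patients are called daily. Those not living alone need more than one room. Households with high-risk members, or with young children and child care responsibilities, are excluded. What may lapse is the explicit isolation instruction only.

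**Conclusion.** The point holds as a minor one. The visible protocol sets isolation at 72 hours, permits CPAP to day 7, and leaves unclear whether isolation applies in between. The uncovered permitted time is 0 days if the closed-door requirement follows CPAP use, and otherwise 2 to 4 days (48 to 96 hours). The 2-day and 3-day figures assume that isolation is counted from delivery and that equipment is ordered at randomization.

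Two stronger conclusions are tempting and should not be drawn. The first is that four days without isolation are established, or that household infections will follow. Four days is the top of a range that includes zero, and nothing in the documents allows harm to be quantified. The second is that the trial's comparisons are compromised. The primary endpoint does not include household infection, so the primary analysis is unaffected. The randomized comparison of conversions remains valid as a comparison of strategies: CPAP with its isolation instructions against control.

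**What to change.** In Section 7.1 item 6, and to the same effect in Section 1.2 under Study Design and under Aim 1, write:

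> Patients in the CPAP arm will isolate for at least 72 hours, and thereafter, in a separate room with the door closed, for as long as CPAP is used, up to day 7.

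In Section 7.1 item 9, add:

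> CPAP may continue beyond 72 hours only if the patient can keep isolating during use.

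The 72-hour minimum has to stay. A rule tied to CPAP use alone would release a patient who stops CPAP early from isolation that the present text requires. Exclusion criterion 1, the sample size, the primary analysis and Fisher's exact test of conversions need no change.

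**Cost.** One sentence in each of four places. Fewer patients may choose to continue CPAP, which may lower the secondary endpoint on continuation beyond 72 hours. The difference in isolation between arms widens slightly in the conversion comparison, so the report should describe that result as CPAP plus isolation versus control.

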#### SCREENING VISIT

Upon reaching out to patient, the coordinator will confirm enrollment eligibility with the patient prior to consenting.

#### 7.3 VISIT 1

Visit 1 is performed by the coordinator. It consists of the following forms:

- Phone consent
- Enrollment Eligibility Form
- ER Admission Data Form
- Demographics and Subject History Form
- Participant Contact Form
- Medications Form
- CPAP and WatchPAT Assignment Form
- PROMIS questionnaire Form
- Randomization Form
- Respiratory Questionnaire Form
- 1. Once the Mount Sinai team has randomized patient, we will email [contact] with demographics and equipment ordered.
- 2. Community surgical will call patient to confirm address and information, they will then initialize the WatchPAT.
- 3. The pin used will be the DOB in the following format: MMDD
- 4. The pin will be written on the WatchPAT box as well
- 5. Community surgical will then deliver the equipment box to the patient. Patient will receive documents to sign via docusign.

- 6. Once delivery has been made, community surgical will notify PI
- 7. Community surgical will register patient on encoreanywhere once patient has been registered it will take approximately 24 hours before we are able to see the patient on our end

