Early Continuous Positive Airway Pressure (CPAP) in COVID-19 Confirmed or Suspected Patients

PI: [name], MPH

NCT04390191

Document Date: 4-21-2020

General Design Issues

This is a prospective, single-center, parallel group, open-label, randomized clinical trial. The primary objective is to evaluate the efficacy and safety of the use of CPAP versus control in COVID-19 suspected or confirmed patients with pneumonia or respiratory illness. The primary efficacy endpoint is a **non-weighted composite endpoint comprised of the following components:**

- All-cause mortality within 14 days of randomization
- Hospital Admission (including ED visit) within 14 days of randomization
- Oxygen saturation less than 90 during the 72-hour observation period from randomization
- Absolute reduction in oxygen saturation of more than 4% during the 72-hour observation period from randomization

Sample Size and Power

Sample size was restricted by the availability of CPAP and the need for rapid answers during the exceptional health care challenges and fluid epidemiological conditions. The table below summarizes the effect sizes (% reduction in the proportion of patients with a negative outcome) that can be detected with sufficient power (>80%) under several scenarios assuming a total sample size of 200 patients (100 per arm) using a two-sided Fisher's exact test at the 0.05 significance level. Preliminary data from the Mount Sinai Health System indicated that about 25% of the COVID-19 positive patients with respiratory distress were sent home and subsequently hospitalized. We assumed that the proportion of patients with a negative outcome in the control group will range between 25% to 50%. Depending on these values, the planned sample size will allow us to detect a relative treatment reduction between 64% to 42% in this range (see table below).

Furthermore, given the short follow-up time for the assessment of the primary outcome and the nature of the primary outcome, we anticipate that we will be able to assess the primary outcome on all patients. We also believe that patients will be supportive of this intervention and compliant with treatment, so sample size was not adjusted for drop-out rates. However, if due to unforeseen circumstances we will conservatively set any missing primary outcome assessment to "negative" or "failure". Power calculations were performed in SAS 9.4 using the PROC POWER function.

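### Both SpO2 components of the primary endpoint run for 72 hours from randomization, but the only SpO2 devices arrive afterwards, so a patient set up at 24 hours has 48 of the 72 hours observed

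*Protocol*

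**What the plan says.** **The endpoint window.** Protocol 1.3 (Endpoints) and SAP General Design Issues list the same four components. Death and hospital admission or ED visit are counted to day 14. The other two are "Oxygen saturation less than 90 during the 72-hour observation period from randomization" and "Absolute reduction in oxygen saturation of more than 4% during the 72-hour observation period from randomization". The origin of both SpO2 windows is explicit: randomization.

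**When the devices arrive.** The Randomization Form belongs to Visit 1, and equipment is requested after that: "Once the Mount Sinai team has randomized patient, we will email" the supplier (Protocol 7.3). The supplier then calls the patient, initializes the WatchPAT and delivers the box. Device set-up is a separate Visit 2 call (7.4 and the Visits Figure). Under 7.1 item 4, orders before noon arrive the same day. For the rest, "Orders placed past noon, CPAP delivery will be done the subsequent day or upto 48 hours if outside the New York area".

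**Where SpO2 values come from.** According to 7.1 item 5, "the oximeter will stay on continuously and the patient will report the saturation to us via follow up survey". Item 13 asks patients to "track their own oxygen saturation using the provided pulse oximeter and report it when we contact them for the 6-12 hour follow up calls/surveys". The WatchPAT adds one 12-hour recording (item 14).

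**When monitoring ends.** Item 9 says "After 72 hours, patients will be asked to discontinue using the CPAP and pulse oximeter" and gives no origin for the 72 hours. Item 11 adds: "The patients can also choose to monitor their oxygen saturation beyond the 72 hours of treatment".

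**Missing data.** SAP Sample Size and Power expects the primary outcome to be assessable in everyone and classes any missing assessment as a failure.

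**The concern.** The endpoint clock starts before there is anything to measure with. Hours between randomization and set-up are inside the window but yield no saturation data. If the CPAP course and the oximetry are timed from set-up, an equal number of hours at the other end are monitored by plan but lie outside the window. A next-day patient who desaturates on the third day of CPAP, still under treatment and still reporting, does not have an SpO2 endpoint event.

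A smaller gap sits beside this. The SAP does not say whether a window seen only in part is a missing assessment. One reading turns every delayed patient into a failure; the other treats unobserved hours as event-free. In an open-label trial with self-reported saturation, that choice should be made before the data are seen.

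**Working it through.** **1. Is there any SpO2 source before set-up?** The oximeter and the WatchPAT are both shipped after randomization. The saturation on the ER Admission Data Form predates randomization and cannot fill the gap. The next-day and 48-hour sentence in item 4 names CPAP, but 7.3 describes a single equipment box, and item 4 itself allows 24-48 hours from discharge for mailing the oximeter and WatchPAT. So the plan provides no reading before set-up.

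**2. Observed hours.** With a delay of d hours from randomization to set-up, observed hours = 72 − d. If the six check-in columns of the Visits Figure (ending at 12, 24, 36, 48, 60 and 72 hours) are timed from set-up, a check-in lies inside the window when its column end + d ≤ 72.

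| d (h) | Observed hours | Share of window | Check-ins inside window |
|---|---|---|---|
| 0 | 72 | 100% | 6 of 6 |
| 12 | 60 | 83% | 5 of 6 |
| 24 | 48 | 67% | 4 of 6 |
| 48 | 24 | 33% | 2 of 6 |

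**3. Does the origin of item 9 matter?** Not for the observed hours. If oximetry stops 72 hours after randomization, a patient set up at 24 hours has 48 hours recorded. If it stops 72 hours after set-up, readings run to 24 + 72 = 96 hours, but those after hour 72 fall outside the endpoint definition. Items 4 to 7 (delivery, instruction, then 72 hours of CPAP) and item 11's reference to hours of treatment favour set-up. Item 9 is therefore not itself the defect; the mismatch is between the endpoint definition and the delivery sequence.

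**4. The SAP's own power figures.** With 100 per arm and a two-sided Fisher's exact test at 0.05, exact power by enumeration for the six columns of the SAP table is 83.0%, 85.4%, 84.3%, 84.4%, 80.9% and 83.3%. The SAP's claim of more than 80% is reproduced.

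**5. Illustration of lost power.** The documents give neither of the next two inputs, so both are assumptions: q, the share of patients set up at 24 hours (the rest at once), and s, the share of negative outcomes that are SpO2-only. Assume also a constant event rate, equal delays in both arms and one-off events. A delayed patient loses 24/72 = 1/3 of SpO2-only events, so each arm's rate is multiplied by k = 1 − s × q / 3.

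| Scenario | s | q | k | Rates | Power |
|---|---|---|---|---|---|
| 40% vs 20% | – | 0 | 1 | 40.0% vs 20.0% | 84.4% |
| 40% vs 20% | 25% | 25% | 0.979 | 39.2% vs 19.6% | 83.3% |
| 40% vs 20% | 50% | 50% | 0.917 | 36.7% vs 18.3% | 79.4% |
| 40% vs 20% | 75% | 100% | 0.750 | 30.0% vs 15.0% | 66.9% |
| 25% vs 9% | – | 0 | 1 | 25.0% vs 9.0% | 83.0% |
| 25% vs 9% | 50% | 50% | 0.917 | 22.9% vs 8.2% | 78.7% |
| 25% vs 9% | 75% | 100% | 0.750 | 18.8% vs 6.8% | 67.2% |

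**6. Relaxing the one-off assumption.** Both components count any occurrence, so a patient who desaturates repeatedly can still be caught in the remaining hours. If half of the patients otherwise lost still register an event (a further assumption), the 50%/50% case for 40% vs 20% has k = 1 − 0.25/6 = 0.958, rates 38.3% vs 19.2%, and power 82.0%.

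**The case against.** The strongest case on the other side has four parts.

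- **The rule for late readings is already fixed.** A reader might infer that the plan leaves open whether saturations after hour 72 count. It does not: both documents exclude them. What is unstated is only how a part-observed window is classified. This objection stands.
- **The fix does not recover the lost hours.** Hours before set-up stay unobserved; the change adds later, on-treatment hours. Nor would observing the early hours restore 84.4%. If CPAP has no effect before set-up, full observation from randomization with s = q = 50% gives 40% vs 20% + 0.25 × 20%/3 = 21.7%, and power of 76.5%. The 84.4% benchmark belongs to a window that covers the full 72 monitored hours. This also stands, and it is why the fix is presented as an improvement in what is counted.
- **The power loss leans high.** Orders before noon arrive the same day, the 48-hour case applies only outside the New York area, repeated desaturations can still be caught, and a desaturation leading to an ED visit, admission or death already counts. So the one-third loss is an upper bound under a constant rate.
- **A fixed window from randomization suits intention-to-treat.** It gives every patient the same calendar period, whereas a window ending after set-up depends on a post-randomization event that, in the CPAP arm, also involves mask fitting. This is a genuine trade-off. It is met by keeping randomization as time zero, using one rule in both arms, and retaining the present window as a sensitivity analysis.

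Two stronger inferences are not supported. The documents do not show that delays differ by arm, so they do not show bias: both arms depend on shipped equipment. Nor do they show that CPAP would be withdrawn early, because item 9 gives no origin and the sequence of steps points to set-up.

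**Conclusion.** The mismatch holds on the text and needs no assumption: set-up at 24 hours leaves 48 of 72 hours observed, and at the 48-hour limit 24 of 72. If the course runs from set-up, planned on-treatment readings are excluded from the primary endpoint. The classification of a part-observed window is undefined.

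The consequence is lost events and some loss of power, of unknown size. In the middle illustration (half of patients set up at 24 hours, half of negative outcomes SpO2-only) power for 40% vs 20% falls from 84.4% to about 79-82%, depending on whether desaturations recur. A reader might infer from the 66.9% row that the trial is seriously underpowered. That figure needs every patient set up at 24 hours, three quarters of negative outcomes to be SpO2-only, and no recurrence; the documents establish none of these. The sample-size calculation is sound on its own inputs. The point is worth correcting but does not invalidate the trial.

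**What to change.** - **Endpoint (Protocol 1.3, SAP General Design Issues).** Define both SpO2 components, in both arms, as running from randomization until 72 hours after the equipment set-up call. Keep the 14- and 28-day endpoints timed from randomization.
- **Procedures (Protocol 7.1 items 8 and 9).** Time the 6-12 hour check-ins, and the request to stop CPAP and the oximeter, from the set-up call.
- **SAP, missing data.** State that a part-observed window is not by itself a missing assessment, and give one rule, the same in both arms, for patients who are never set up.
- **SAP, reporting.** Report the delay from randomization to set-up by arm, and give the window of 72 hours from randomization as a sensitivity analysis.

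**Cost.** A phrase in each endpoint definition, a line in 7.1 and a few SAP sentences. The check-ins and oximetry are already planned; the set-up time must be recorded. The SpO2 window would end at a patient-specific time after randomization, from 72 to about 48 + 72 = 120 hours, and hours before set-up would remain unobserved. Because this changes two primary components, it needs DMC review and approval (Protocol 1.5) and submission to the IRB as an amendment (Protocol 3.2).
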